5.4 Cost Analysis

All patients in the study population will have a total cost calculated for their cardiac surgery hospital stay. This cost will be determined by tabulating cost of the *Prehab* intervention and different aspects of inpatient resource utilization for each study participant, and assign the best estimate of cost for each component. Pre- and post-operative hospital *LOS* on the hospital ward along with *LOS* in the cardiac surgery intensive care unit (*CS-ICU*) are expected to be the major drivers of a patient’s overall cost. A sensitivity analysis will also be performed to account for uncertainty in any of the costs by simulating several different scenarios, and developing a range of cost estimates for each patient.

6 Data Management

The data management and analysis will be undertaken by the St. Boniface Hospital/I.H. Asper Clinical Research Institute. The principal means of data collection and data processing will be via electronic data entry at each site. Data will be exported to the St. Boniface Hospital/I.H. Asper Clinical Research Institute stripped of any patient identifiers. Each patient will be given a site and an anonymous unique study number.

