3.4.9 Data Collection Instruments – The Data Collection Package

The following variables will be collected for participants in both arms of the trial, as well as the registry. This information will be obtained from existing electronic databases as well as hospital charts.

1. Patient Demographics/Hospital Length of Stay
2. Preoperative Cardiac Information
3. Preoperative Comorbidities
4. Lab Results (pre and post-op)
5. Echocardiogram Information
6. Angiogram Information
7. Procedure Information

8. Medications (pre and post-op)
9. Post-Operative Delirium
10. Post-Operative Complications
11. 30 Day Readmission
12. 12 Month Readmission

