Health Care Professionals	Utilization of the Canadian Cardiovascular Critical Care (CANCARE) Society Network to identify the lack of peri-operative protocols for frail elderly persons and care of the cardiac surgery patient (Lamarche et al., 2012)	
Improving Outcomes:
 
We have identified Canadian centers capable of engaging in multicenter Prehab RCT, including Winnipeg, Halifax and Saint John. This includes both academic and non-academic cardiac surgery centers.
	
We plan to complete a Phase II, multicentre RCT examining the outcomes of patients undergoing Prehab during the patient journey from time of surgical referral to time of surgical procedure.
	
We plan to determine the cost effectiveness of the PREHAB model of care to determine if the intervention reduces different aspects of inpatient resource utilization .

Health Care System	We have completed a systematic review of current outcome(s) of frail elderly persons undergoing cardiac surgery and have determined that frailty is associated with increased mortality and other negative outcomes (see tables 1 & 2)	
Develop, Evaluate and Disseminate
 
 1. We have engaged local community cardiac rehabilitation programs in 3 provinces. 2. We have engaged a local regional health authority for study evaluation and developed an integrated knowledge translation plan (IKT) for patients/patient families, primary and specialist health care providers to ensure program sustainability 	
Improving care across the continuum:
 
We have already engaged and will continue to engage a national cardiac rehabilitation organization (CACR) to support our project through network development, patient advocacy, knowledge translation and knowledge transfer to the patients, their families and the inter-disciplinary healthcare teams involved in the care of the frail elderly person with cardiac disease.
	
Our long term plan is to access administrative data to determine if the Prehab intervention helps to reduce health care utilization for patients over a 1 and 5 year period. However, this aspect is a next stage beyond the scope of the current proposal.

“The PREHAB Study” (Pre-operative Rehabilitation for reduction of Hospitalization After coronary Bypass and valvular surgery.)

Table 2 - Characteristics of Included Studies In Frailty and Cardiac Surgery Systematic Review

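### The cost analysis in section 5.4 stops at the surgical stay although readmissions are collected, so any difference in readmission between arms is left out of the cost comparison.

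*Combined protocol and SAP*

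**What the plan says.** Section 5.4 (Cost Analysis) sets the scope in its first sentence: "All patients in the study population will have a total cost calculated for their cardiac surgery hospital stay". The total is built from the cost of the Prehab programme and "different aspects of inpatient resource utilization for each study participant, and assign the best estimate of cost for each component". Ward stay before and after the operation and stay in the cardiac surgery ICU "are expected to be the major drivers of a patient’s overall cost". On uncertainty it says: "A sensitivity analysis will also be performed to account for uncertainty in any of the costs by simulating several different scenarios". It names no time horizon, no readmission component and no method for comparing the arms.

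Section 3.4.9 (Data Collection Instruments) states: "The following variables will be collected for participants in both arms of the trial, as well as the registry". Its list includes "30 Day Readmission" and "12 Month Readmission". Section 3.6 adds that returns to ICU and hospital are held in institutional databases. Cost analysis is item 7 of the secondary outcomes in section 5.1.2. In the cost-effectiveness column of Table 1 the plan says: "We plan to determine the cost effectiveness of the PREHAB model of care", and the same sentence goes on to define the question as whether inpatient resource use falls.

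**The concern.** The primary outcome is the proportion of patients staying more than 7 days, and section 5.4 expects length of stay to drive cost. When an intervention aims to shorten the stay and the count ends at discharge, each index day saved is credited and each day spent in hospital after a return is ignored. Suppose a patient goes home 2 days earlier and is then readmitted for 5 days. Section 5.4 as written records 2 days saved, when 3 more days were used. The reverse error is equally possible. If better preoperative condition means fewer returns to hospital, the index stay alone misses part of the benefit.

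The sensitivity analysis does not help, because it varies the costs assigned and not the period over which they are counted. At stake is whether the trial's one economic result describes hospital use or only use up to first discharge.

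**Working it through.** Section 5.4 states no cost figure, so there is none to reproduce. The check has two parts.

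**1. Scope of cost against data collected**

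| Item | Collected? | In the 5.4 cost? |
|---|---|---|
| Prehab programme | yes (5.4) | yes |
| Index ward and ICU stay | yes (3.4.3, 3.6) | yes |
| 30-day readmission | yes, both arms (3.4.9) | not named |
| 12-month readmission | yes, both arms (3.4.9) | not named |

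The analysis text for objectives 1 and 2 in section 5.2 does not use the readmission items either.

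**2. Size of the omission, in bed-days**

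Inputs:
- Index days saved, *s*. The introduction of the appended pilot article cites a reduction of 1 day from an earlier randomised trial. Section 3.1.1.1 gives medians of 8 days in frail and 6 in non-frail patients, a gap of 8 − 6 = 2 days. That gap is not a treatment effect and serves only as a second scenario.
- Difference in readmission risk between arms, *d*: assumed 2, 5 or 10 percentage points.
- Days per readmission, *L*: assumed 3 to 10, equal in both arms.

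Bed-days per patient left out of the comparison = *d* × *L*:

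| *d* | *L* = 3 | *L* = 5 | *L* = 7 | *L* = 10 |
|---|---|---|---|---|
| 2 points | 0.02 × 3 = 0.06 | 0.10 | 0.14 | 0.02 × 10 = 0.20 |
| 5 points | 0.05 × 3 = 0.15 | 0.25 | 0.35 | 0.05 × 10 = 0.50 |
| 10 points | 0.10 × 3 = 0.30 | 0.50 | 0.70 | 0.10 × 10 = 1.00 |

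Against a 1-day saving these are 6–20%, 15–50% and 30–100%. Against a 2-day saving the shares are halved.

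Excess readmission in the Prehab arm that would cancel the saving = *s* / *L*:

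| *s* | *L* = 3 | *L* = 5 | *L* = 7 | *L* = 10 |
|---|---|---|---|---|
| 1 day | 1/3 = 33.3 points | 20.0 | 14.3 | 1/10 = 10.0 |
| 2 days | 2/3 = 66.7 points | 40.0 | 28.6 | 2/10 = 20.0 |

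The first table applies with either sign. If Prehab patients are readmitted less often, the same quantities are savings that go uncounted.

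**The case against.** Four arguments on the other side deserve weight.

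- *The wording on inpatient resource use could include readmissions.* It could, but the sentence before it ties the total to the surgical stay. If readmissions are meant, one clause would settle it.
- *The longer horizon is openly deferred.* Table 1 places health care utilization over 1 and 5 years, from administrative data, beyond the present proposal. This stands as a reason not to insist on 12-month cost as the main result. It does not explain leaving out readmissions that the trial itself collects, above all those within 30 days.
- *Discharge is standardised.* Section 3.4.1 provides a daily check of readiness for discharge. Its stated purpose is to deal with non-medical delay, so it gives some consistency but does not address returns to hospital.
- *Readmission days may not be recorded.* Section 3.4.9 gives only item labels. This stands, and it bears on the fix.

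A reader might also infer three stronger things that the documents do not support. First, that the analysis is biased in favour of Prehab: nothing in the documents fixes the sign, and an intervention meant to improve preoperative condition could lower readmission. Second, that all readmission use is the error. With 15–20% of patients readmitted for 5–8 days (assumed), 0.15 × 5 = 0.75 to 0.20 × 8 = 1.6 days per patient go uncosted, but that is gross use in both arms and only the difference between arms affects the comparison. Third, that the plan promises a cost-utility analysis and fails to deliver it: Table 1 frames its question as inpatient resource use, and section 5.1.2 lists only a cost analysis.

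**Conclusion.** The point holds as a minor one. As written, section 5.4 costs the Prehab programme and the surgical stay and leaves out readmissions collected in both arms. The between-arm cost difference is wrong to the extent that readmission differs by arm, in either direction, and unaffected by readmission if use after discharge is equal.

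Under the assumed ranges the omission is 0.06 to 1.00 bed-days per patient. That can be material against a 1-day saving, but cancelling such a saving outright needs an excess of at least 10 points with 10-day readmissions, and about 33 points with 3-day readmissions. These figures rest on assumed rates and lengths, on equal length of readmission in the two arms, and on bed-days standing in for cost. Only a secondary outcome is touched.

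**What to change.** In section 5.4:

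- Define hospital cost per randomised patient as Prehab programme + index stay + readmissions to 30 days, and state whether the 30 days run from surgery or from discharge.
- Compare mean cost by arm with a bootstrap confidence interval.
- Report index-stay cost as a separate component, so that the result now planned remains visible.
- Give cost including readmissions to 12 months as a supportive analysis.
- Confirm that readmission dates or days are captured. If they are not, label the result index-admission cost and do not describe it as cost-effectiveness, in Table 1 or in reports.

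Two further extensions are optional and the point does not depend on them. One is relating cost to EQ-5D. The other is adding admissions between randomisation and surgery; here the twice-weekly stability check by the rehabilitation team (section 4) may make events easier to detect in the Prehab arm.

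The price is a change of SAP wording, unit costs for readmission days and a somewhat wider confidence interval. If readmission days are not yet recorded, extra data capture is needed as well.

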6.1 Site Monitoring

Site monitoring will be performed by the site leads at their respective sites.

“The PREHAB Study” (Pre-operative Rehabilitation for reduction of Hospitalization After coronary Bypass and valvular surgery.)

6.2 Data Recording and Document Retention

De-identified data will be entered by each participating site into an electronic REDCap eCRF. The data will be housed in a secure server located at the University of Manitoba Faculty Of Medicine. Each site will only be able to access their own data and only the project manager and principal investigator will be able to view identifying data. Each person having access to the REDCap software will be issued their own unique number generator key fob which will allow for audits of data entry. All data collected will be by the study will be kept for a minimum of 7 years or as otherwise required by regulatory agencies.

6.3 Data quality assurance

Data entered by each site will be password-protected and the ability to access or change data prior to locking of the database will be restricted to the project manager. Once initial data collection has been completed, missing data and implausible values will be identified using predetermined objective criteria, and queries resolved through direct communication with sites if required. This data cleaning process will be overseen by the *PREHAB* management committee. Treatment of outliers and missing data will be in accordance with the statistical analysis plan.

6.4 Funding

Canadian Institutes for Health Research (CIHR)

[figure not shown]
Term and Budget Requested: \$619,784 (4-year term)

7 Participating Sites

The study will be conducted at four academic, tertiary care hospitals (St. Boniface Hospital, Winnipeg, MB, Queen Elizabeth II Health Sciences Centre, Halifax, NS, Montreal Heart Institute, Montreal, QC, Quebec heart and lung institute, Saint-Foy, QC) and one non-academic hospital (Saint John Regional Health Centre, Saint John, NB) that perform cardiac surgery

8 Operations Structure

8.4 Coordinating Centre

The coordinating centre for this project will be the St. Boniface Hospital/I.H. Asper Clinical Research Institute located in Winnipeg, Manitoba.

8.7 Research Coordinator

The research/project coordinator will be responsible for the day-to-day coordination of activities between the three sites and will be based out of the coordinating center (St. Boniface General Hospital, Winnipeg).

- Ensuring ethics submissions are up-to-date and properly stored.
- Responsible for data handling and will liaise with the other two study sites.
- Will travel from Winnipeg to Halifax and St. John project sites to train the fee-for-service research staff located at those sites.
- Coordinate weekly teleconferences to support study implementation.
- Dissemination of the overall study

PROJECT COORDINATOR AND SITE COORDINATOR RESPONSIBILITIES	
Phase 1: Planning	
• Coordinate study planning activities• Arrange stakeholder/researcher meetings• Complete research ethics for the overall project and work with sites to complete local ethics applications/access committee submissions• Orientate site personnel
Phase 2: Implementation	
• Coordinate study implementation for all sites.• Make initial contact with potential participants/screen/recruit in Winnipeg.• Complete baseline, pre-operative and follow-up measures/assessments on participants in Winnipeg.• Data entry, to include baseline, pre-operative and follow-up measures; chart reviews; site data.
Phase 3: Evaluation/ Dissemination	
• Coordinate study evaluation/dissemination.• Update review of literature.

	
• Participate in knowledge dissemination.
--	---

8.7 Research Assistants

Site Coordinator #1 (Halifax, Nova Scotia): In order to implement the proposed study in Halifax, we plan to hire a 0.5 part time Site Coordinator for 2 years.

Site Coordinator #2 (Saint John, New Brunswick): In order to implement the proposed study in Saint John, we plan to hire a 0.5 part time Site Coordinator for 2 years.

Site Coordinator #3 (Montreal, Quebec): In order to implement the proposed study in Montreal, one year into study launch, we plan to hire a 0.5 part time Site Coordinator for 1 year.

Site Coordinator #4 (Quebec City, Quebec): In order to implement the proposed study in Quebec City, two years into study launch, we will utilize their existing infrastructure for a minimum of 1 year.

8.8 Students

Master’s *Graduate Student*: Under the supervision of the [name], the Graduate Student will work directly on the proposed project to: i) conduct a review of the literature to guide the development and refinement of the recruitment and screening approaches and to conduct the project evaluation; ii) work with the Program Coordinator to collect data by administering surveys/questionnaires and collect objective measures of physical activity; iii) liaise with the cardiac rehab sites to facilitate project outcomes.

Postdoctoral fellow: [name] has recruited [name] to complete a postdoctoral training program under his mentorship and she will devote 25% of her time to this project. Both Drs. [name] and [name] will support her application for the Integrated and Mentored Pulmonary and Cardiovascular Training (IMPACT) program, a CIHR Strategic Training Program in Health Research training program at the St. Boniface Hospital. The overall objective of the IMPACT program is to create the next generation of investigators with the capacity to generate scientific knowledge and, equally importantly, with the skills and linkages to rapidly advance those discoveries to clinic and health care systems. Notably, [name] is the Program Director for the IMPACT program at the University of Manitoba; whereas, [name] has specifically mentored several trainees within the program. As a result, [name] and [name] (Dalhousie) will co-mentor [name] (postdoctoral fellow).

[name] will recruit two B.Sc. Med students from the Faculty of Medicine, University of Manitoba to work on the Prehab project. Additionally, [name] will recruit two undergraduate students from the Faculty of Kinesiology and Recreation Management, University of Manitoba for a Directed Studies Research Internship for course credit so they can work directly on the project. [name] will

“The PREHAB Study” (Pre-operative Rehabilitation for reduction of Hospitalization After coronary Bypass and valvular surgery.)

also supervise a research fellow, [name], at Dalhousie University. He will contribute 100% of his time to this project.

9 Project Timeline

April 2, 2014 to July 1, 2014 (Ethics Submission/Project Coordination)

Obtain all relevant approvals from internal and external ethics boards. Assign duties and responsibilities to all individuals involved in the project.

July 1, 2014 to October 1, 2014

Begin holding focus groups to identify perceptions about physical activity in frail patients and their families. After an initial concentrated focus group session, we plan to continue ongoing sessions with key stakeholders as part of an integrated knowledge translation process.

October 1, 2014 to December 1, 2015 (Patient Recruitment)

Final goal is to recruit 244 total participants (122 individuals in each cohort).

March 1, 2016 (Recruitment and Procedures Completed)

Anticipated date by which all recruited patients will have undergone cardiac procedure and have been discharged from hospital. Primary outcome (hospital length of stay) is available.

June 1, 2016 (All Patients Completed 3-Month Follow-Up)

Anticipated date by which all recruited patients will be eligible for 3-month follow-up and quality of life questionnaire.

March 1, 2017 (All Patients Completed 1-Year Follow-Up)

Anticipated date by which all recruited patients will be eligible for 1-year follow-up and quality of life questionnaire.

March 1, 2017 (Data Analysis and Manuscript Development)

Preliminary data analysis will be conducted, drafts of manuscripts will be developed, iKT activities planned and performed.

May 1, 2017 (Project Completion Date)

All results have been finalized, manuscripts and abstracts have been submitted to various sources. Half-day symposium, joint with CACPR finalized.

9.1 Research Deliverables and Milestones

We anticipate the *PREHAB* study will require 3.5-years to complete (see Table below).

9.2 Preliminary Project Schedule

Timeframe	Milestone	Detail
April – Oct., 2014	
Continue with weekly teleconferencesFinalization of DSMB terms of referenceHREB protocol submissions to each of the sites	Following a meeting at the Canadian Cardiovascular Congress in October, 2013, We have held a series of teleconferences to: (1) Create a HREB template based on the successful previous submissions (2) Begin the process of nominating a three member data safety and monitoring board (DSMB) panel to review all adverse/severe adverse

“The PREHAB Study” (Pre-operative Rehabilitation for reduction of Hospitalization After coronary Bypass and valvular surgery.)

	
 • iKT elements 	events. We will draft a formal terms of reference with a plan to have meetings every six months via teleconference with the principal investigator. (3) Will begin holding focus groups to identify perceptions about physical activity in frail elderly patients and their families. After initial concentrated focus group sessions, we will continue ongoing sessions with key stakeholders as part of our iKT process.
Oct., 2014	Recruitment Begins	We plan to allow for a 14-month recruitment period for initial randomization of patients (see Figure 5)
Jan., 2015	
 • 3-month follow-up begins 	This is will allow for the 8 week Prehab program, surgery and 12 week follow-up (to coincide with the follow-up visit with the patient’s surgeon).
Oct., 2015	
 • 1-year follow-up begins 	1-year follow up for exercise test and quality of life questionnaire.
March, 2016	
 • Recruitment and Procedures Completed 	Anticipated date by which all recruited patients will have undergone cardiac procedure and have been discharged from hospital. Primary outcome (hospital length of stay) is completely available.
June, 2016	
 • All Patients Completed 3-month follow-up 	Anticipated date by which all recruited patients will be eligible for 3-month follow-up and quality of life questionnaire.
March, 2017	
 • All Patients Completed 1-Year Follow-Up 	Anticipated date by which all recruited patients will be eligible for 1-year follow-up and quality of life questionnaire.
March, 2017 – May, 2017	
 • Data analysis/proposed publications • iKT elements • Peer review grant preparation (CIHR) 	Data analysis will be conducted, drafts of manuscripts will be developed, iKT activities planned. Abstract preparation for presentation by trainees at scientific meetings. Initiation of planning with the CANCARE Society and CACR for educational sessions.

10 Project Impact

10.1 Project relevance and impact

The geriatric population is one of the fastest growing demographics undergoing cardiac surgery in North America.(1)(2) With this, the geriatric syndrome, defined as a “constellation of symptoms and signs [that] describe the heterogeneous response of older adults to physiological and metabolic challenges,”(3) has become an important consideration in patients undergoing cardiac surgery. To date, no high-quality study has prospectively examined the impact of preoperative cardiac rehabilitation in the frail-elderly undergoing cardiac surgery and represents a noticeable knowledge gap.

The *PREHAB* study is specifically aimed to improve the care and establish best practice in frail elderly patients undergoing high-risk cardiac surgery procedures through a rigorous evaluation of the utilization of an inter-disciplinary and multimodal patient optimization protocol. Importantly, we have

“The PREHAB Study” (Pre-operative Rehabilitation for reduction of Hospitalization After coronary Bypass and valvular surgery.)

also planned for a detailed study analysis by key stakeholders at the health region level to determine optimal methodologies to implement this program following the completion of this investigation. Reducing anxiety, improving exercise capacity, promoting a healthy lifestyle that is durable (i.e. long-lasting) and improving *HRQoL* in the elderly are the over-riding goals of this endeavour. This investigation directly fits with the Network’s Strategic Research Priorities of improving clinical outcomes in frail elderly patients.

